6.4 Participant numbering, treatment assignment, randomization

6.4.1 Participant numbering

Each participant is identified in the study by a Participant Number (Participant No.), that is assigned when the participant is first enrolled for screening and is retained as the primary identifier for the participant throughout his/her entire participation in the trial. The participant no. consists of the Center Number (Center No.) (assigned by Novartis to the investigative site) with a sequential participant number suffixed to it, so that each participant is numbered uniquely across the entire database. Upon signing the informed consent form, the participant is assigned to the next sequential Participant No. available by the Investigator. The Investigator or his/her staff will contact the IRT and provide the assigned participant study identification number along with the requested identifying information to register the participant into IRT. The site must use the eCRF with the matching participant number from the electronic data capture (EDC) system to enter data.

If an enrolled participant fails to be assigned to treatment for any reason, the IRT must be notified within 2 days that the participant was not assigned to treatment. The reason for not being assigned to treatment will be entered into the appropriate eCRFs. If the participant is re-screened at a later date, a new Participant No. will be assigned.

6.4.2 Treatment assignment, randomization

This is an open label study. There will be no treatment blinding.

6.5 Dose escalation and dose modification

Dose escalation and modifications are not permitted in this study.

6.5.1 Dose escalation guidelines

Not applicable.

6.5.2 Follow-up for toxicities

Not applicable.

6.5.3 Drug Interruptions

Conditions/events that may lead to study drug interruptions based on Investigator judgment and overall clinical assessment include:

- reported serious adverse event;
- emergency medical condition, unplanned hospitalization involving use of excluded concomitant medications;
- abnormal laboratory value(s) or abnormal test or examination result(s)

Should the participant interrupt the study drug for whatever reason, the re-start decision should be made on a case-by-case basis (refer to [Section 6.6.1](#)). Should the Investigator decide, after informing the Sponsor, to re-initiate treatment with study drug, depending on the duration of the interruption, the first dose at re-start may need to take place at the study site to ensure observation in a similar manner as on Baseline/Week 0 (Day 1).

The reason for interruption of treatment and date of interruption should be appropriately documented in the source documents as well as in the appropriate eCRF.

6.6 Additional treatment guidance

6.6.1 Treatment compliance

The Investigator must promote compliance by instructing the participant to take the study drug exactly as prescribed and by stating that compliance is necessary for the participant's safety and the validity of the study. The participant must also be instructed to contact the Investigator if he/she is unable for any reason to take the study drug as prescribed. Compliance will be assessed by the Investigator and/or study personnel at each visit. Participant compliance should be at least 80%. The Investigator and/or study personnel will counsel the participant if compliance is below 80% and will determine (in consultation with Novartis) if the participant will be removed

from the study due to lack of compliance with study drug. Study drug accountability will also be determined by the site monitor while performing routine site/virtual visits and at the completion of the study. This information should be captured in the source document at each visit. All study drug dispensed and returned must be recorded in the Drug Accountability Log.

6.6.2 Recommended treatment of adverse events

At present there is insufficient information to provide specific recommendations regarding treatment of adverse events (AEs) beyond standard clinical care.

Medication used to treat adverse events (AEs) must be recorded on the appropriate CRF.

6.6.3 Emergency breaking of assigned treatment code.

Not applicable.

7 Informed consent procedures

Eligible participants may only be included in the study after providing (witnessed, where required by law or regulation), IRB/IEC-approved informed consent.

If applicable, in cases where the participant's representative(s) gives consent (if allowed according to local requirements), the participant must be informed about the study to the extent possible given his/her level of understanding. If the participant is capable of doing so, he/she must indicate agreement by personally signing and dating the written informed consent document.

Informed consent must be obtained before conducting any study-specific procedures (e.g. all of the procedures described in the protocol). The process of obtaining informed consent must be documented in the participant source documents.

Novartis will provide to investigators in a separate document a proposed informed consent form that complies with the ICH E6 GCP guidelines and regulatory requirements and is considered appropriate for this study. Any changes to the proposed consent form suggested by the investigator must be agreed by Novartis before submission to the IRB/IEC.

Information about common side effects already known about the investigational treatment can be found in the USPI and Investigator's Brochure (IB). This information will be included in the participant informed consent and should be discussed with the participant during the study as needed. Any new information regarding the safety profile of the investigational drug that is identified between IB updates will be communicated as appropriate, for example, via an investigator notification or an aggregate safety finding. New information might require an update to the informed consent and then must be discussed with the participant.

The following informed consents are included in this study:

- Main study consent, which also includes:
 - A subsection that requires a separate signature for the 'Optional Consent for Additional Research' to allow future research on data/samples (e.g. additional new [REDACTED], MRI scans) collected during this study

- Potential for additional efficacy and safety assessments that will be evaluated during the optional 12-month open-label extension for up to 30 months
- An Optional Biomarker Consent for those participants who opt into additional biomarker sample analysis provided from cerebral spinal fluid (CSF)
- As applicable, Pregnancy Outcomes Reporting Consent for female subjects who took study treatment
- As applicable, Pregnancy Outcomes Reporting Consent for the female partners of male participants who took study treatment

Women of childbearing potential must be informed that taking the study treatment may involve unknown risks to the fetus if pregnancy were to occur during the study and agree that in order to participate in the study they must adhere to the contraception requirements.

A copy of the approved version of all consent forms must be provided to Novartis after IRB/IEC approval.

Participants might be asked to complete an optional questionnaire to provide feedback on their clinical trial experience.

As per [Section 4.6](#), during a Public Health emergency as declared by Local or Regional authorities i.e. pandemic, epidemic or natural disaster, that may challenge the ability to obtain a standard written informed consent due to limits that prevent an on-site visit, Investigator may conduct the informed consent discussion remotely (e.g. telephone, videoconference) if allowable by a local Health Authority.

Guidance issued by local regulatory bodies on this aspect prevail and must be implemented and appropriately documented (e.g. the presence of an impartial witness, sign/dating separate ICFs by trial participant and person obtaining informed consent, etc.).

8 Assessment schedule and assessments

The Assessment Schedule ([Table 8-1](#)) lists all of the assessments when they are performed. All data obtained from these assessments must be supported in the participant's source documentation.

Participants should be seen for all visits/assessments as outlined in the assessment schedule ([Table 8-1](#)) or as close to the designated day/time as possible. Missed or rescheduled visits should not lead to automatic discontinuation.

Participants who discontinue from study treatment and study participation, and do not continue on any MS DMT, are to return for the end of study visit as soon as possible and attend safety follow-up visits as indicated in the Assessment Schedule ([Table 8-1](#)). Healthy control participants will not have a safety evaluation post end of study.

Participants who discontinue from study or withdraw their consent/oppose the use of their data/biological samples should be scheduled for a final evaluation visit if they agree, as soon as possible, at which time all of the assessments listed for the final visit will be performed. At this final visit, all dispensed investigational product should be reconciled, and the adverse event and concomitant medications not previously reported must be recorded on the CRF.

[figure not shown]
The “X” in the table denotes the assessments to be recorded in the clinical database or received electronically from a vendor. The “S” in the table denotes the assessments that are only in the participant’s source documentation and do not need to be recorded in the clinical database.

As per [Section 4.6](#), during a Public Health emergency as declared by Local or Regional authorities i.e. pandemic, epidemic or natural disaster that limits or prevents on-site study visits, alternative methods of providing continuing care may be implemented by the investigator as the situation dictates. If allowable by a local Health Authority and depending on operational capabilities, phone calls, virtual contacts (e.g. tele consult) or visits by site staff/ home nursing staff to the participant’s home, can replace on-site study visits, for the duration of the disruption until it is safe for the participant to visit the site again.

[figure not shown]

Table 8-1 Assessment Schedule

[figure not shown]
[figure not shown]
Name	Scr	BSL/ Wk0	Wk 1	Wk 2	Wk 4	M3	M6	M9 ⁶	M12	M15 ⁶	M18	M21 ⁶	M24 ⁶	M27 ⁶	M30/ EOS	100- day Safety Follow -up ¹²	USV ⁴
Days: Window:	-28	1 (+3)	7 (±1)	14 (±1)	28 (±3)	90 (±3)	180 (±3)	270 (±3)	360 (±3)	450 (±3)	540 (±3)	630 (±3)	720 (±3)	810 (±3)	900 (±3)		
Informed Consent ^x	O,H										O,H ¹³						
Patient Demographics ^x	O,H																
Medical History ^x	O,H																
Smoking Status	O,H										O,H				O,H		
MS History ^x	O																
Inclusion/ Exclusion/ Criteria ^x	O,H	O															
Height/ Weight ^x	O,H	O															
Dispense Study Drug ^x		O ⁷	O	O	O	O	O	O	O	O	O	O	O	O			
Collect Study Drug/ Drug Account-ability			O	O	O	O	O	O	O	O	O	O	O	O	O		O

[figure not shown]
Name	Scr	BSL/ Wk0	Wk 1	Wk 2	Wk 4	M3	M6	M9 ⁶	M12	M15 ⁶	M18	M21 ⁶	M24 ⁶	M27 ⁶	M30/ EOS	100- day Safety Follow -up ¹²	USV ⁴
Days: Window:	-28	1 (+3)	7 (±1)	14 (±1)	28 (±3)	90 (±3)	180 (±3)	270 (±3)	360 (±3)	450 (±3)	540 (±3)	630 (±3)	720 (±3)	810 (±3)	900 (±3)		
Sc Self-injection Training (participant and/or caregiver) ^s		O															
Study drug self- injection (at- home or at site) ^x . 16, 17			O	O	O	O	O	O	O	O	O	O	O	O	O		
Prior and Concomitant Meds ^x	O,H	O,H	O,H	O,H	O,H	O,H	O,H	O,H	O,H	O,H	O,H	O,H	O,H	O,H	O,H	O	O,H
Non-drug therapies ^x	O,H	O,H	O,H	O,H	O,H	O,H	O,H	O,H	O,H	O,H	O,H	O,H	O,H	O,H	O,H	O	O,H
Vital Signs ^{x,7}	O,H	O,H	O,H	O,H	O,H	O,H	O,H		O,H		O,H				O,H		O,H
Physical Exam ^s	O ³ ,H	O,H	O,H	O,H	O,H	O,H	O,H		O,H		O,H				O,H		O,H
Adverse Events ^{x,4}	O,H	O,H	O,H	O,H	O,H	O,H	O,H	O,H	O,H	O,H	O,H	O,H	O,H	O,H	O,H	O	O,H

Name	Scr	BSL/ Wk0	Wk 1	Wk 2	Wk 4	M3	M6	M9 ⁶	M12	M15 ⁶	M18	M21 ⁶	M24 ⁶	M27 ⁶	M30/ EOS	100- day Safety Follow -up ¹²	USV ⁴
Days: Window:	-28	1 (+3)	7 (±1)	14 (±1)	28 (±3)	90 (±3)	180 (±3)	270 (±3)	360 (±3)	450 (±3)	540 (±3)	630 (±3)	720 (±3)	810 (±3)	900 (±3)		
MS Relapse Assessment ^{x, 2}	○	○	○	○	○	○	○	○	○	○	○	○	○	○	○	○	○
Labs (hematology, biochemistry) ^x	○										○				○	○	○

Name	Scr	BSL/ Wk0	Wk 1	Wk 2	Wk 4	M3	M6	M9 ⁶	M12	M15 ⁶	M18	M21 ⁶	M24 ⁶	M27 ⁶	M30/ EOS	100- day Safety Follow -up ¹²	USV ⁴
Days: Window:	-28	1 (+3)	7 (±1)	14 (±1)	28 (±3)	90 (±3)	180 (±3)	270 (±3)	360 (±3)	450 (±3)	540 (±3)	630 (±3)	720 (±3)	810 (±3)	900 (±3)		
Hepatitis B ^{S, 9}	O																
HIVs, ⁹	O																
Coagulation ^{S, 9}	O	O									O				O		O
Dipstick urinalysis ^{X, 10}	O	O									O				O		O
Serum β-hCG in women of childbearing potential ^{S, 3}	O	O															O
Urine β-hCG in women of childbearing potential ^{S, 3}			O	O	O	O	O	O	O	O	O	O	O	O	O		O
MRI ^{X, 14, 18}	O,H						O,H		O,H		O,H				O,H		O
Columbia Suicide Severity Scale (C- SSRS) ^{X, 15}	O	O	O	O	O	O	O		O		O				O		
PROs ^X (NeuroQOL™, PDDS)		O,H	O,H	O,H	O,H	O,H	O,H		O,H		O,H				O,H		

Name	Scr	BSL/ Wk0	Wk 1	Wk 2	Wk 4	M3	M6	M9 ⁶	M12	M15 ⁶	M18	M21 ⁶	M24 ⁶	M27 ⁶	M30/ EOS	100- day Safety Follow -up ¹²	USV ⁴
Days: Window:	-28	1 (+3)	7 (±1)	14 (±1)	28 (±3)	90 (±3)	180 (±3)	270 (±3)	360 (±3)	450 (±3)	540 (±3)	630 (±3)	720 (±3)	810 (±3)	900 (±3)		
Optional Trial Feedback Questionnaire ^S		O,H					O,H				O,H				O,H		
Participant Thank You Letter ^S		O,H									O,H				O,H		

O = Ofatumumab participant

H = Healthy Control

X = assessment to be recorded in the clinical database or received electronically from a vendor

S = assessment to be recorded in the source documentation only

■ [Redacted]

² Relapse assessment will be performed in scheduled, as well as unscheduled visits as deemed necessary by the Investigator or designee. Assessment can be done on site or via remote procedures

³ Urine β-hCG will be conducted monthly, at home, as well as, at defined clinical visits (scheduled and unscheduled)

[Redacted]

⁴ Assessment during an unscheduled visit will be performed as deemed necessary by the investigator, **except** for vital signs and evaluation of AE, which are mandatory at each visit

⁶ Participants are not required to come to the study site. Remote contact with participants, by site staff around the time of at-home, self-administration of ofatumumab should query about any new or worsening symptoms warranting an unscheduled visit, MS relapse, compliance with study treatment [REDACTED], adverse events, and compliance with contraception requirements (when applicable). The method of contact can be via telephone, email, video conference or text message depending on the preference of each participant

⁷ For the first injection, vital signs should be obtained 30-60 minutes before sc injection and again approximately 60 minutes post-injection

⁸ All lab assessments should be taken prior to dosing at the Day 1 visit. For any later biomarker visits, if the visit coincides with the day the monthly injection is scheduled, the subject should not take the injection in the morning before coming to the site so that the biomarker sample can be drawn before the injection

⁹ Labs must be drawn to allow adequate time for results to be obtained before first study drug administration to ensure participant's eligibility

¹⁰ Urine dipstick: If abnormal send full urinalysis to central laboratory

¹² Data for safety follow-up visit will be captured in source documentation only. Safety follow-up participants are not required to come to study site and lab assessments should be done locally

¹³ Only for participants continuing onto the 12-month open-label extension period

¹⁴ Gadolinium will not be given to healthy controls and gadolinium enhanced T1 MRI imaging will not be conducted in healthy controls

¹⁵ The C-SSRS must be administered at either screening or baseline, then at every on-site visit thereafter until End of Study (EOS)

¹⁶ Administration of ofatumumab (at study site or at home) should occur after the study visit assessments are performed, if on the same day of the study visit

¹⁷ Study drug self-injection (at-home or on-site) will be performed **monthly**, beginning at Week 4, by all ofatumumab participants

¹⁸ MRI assessment must be completed within +/-7 days of the visit

8.1 Screening

Screening

A participant who enters screening but is determined not to be eligible will be considered a screen failure. The Investigator may consider re-screening the participant later if he/she believes that the participant's condition has changed, and he/she may potentially be eligible. In this case, a new participant number will be allocated to the participant and he/she will need to re-perform all screening procedures except for MRI. The original MRI may be used during rescreening if the rescreening occurs within 3 months of the original MRI date. Requests from the investigator/site staff to rescreen patients will be handled on a case-by-case basis, with Clinical Trial Lead approval required, prior to rescreening. A participant may be re-screened only once. A minimum of 24 hours must elapse between screen failure and re-screening. If a participant is re-screened, a new ICF must be obtained, and a new participant number issued prior to conducting any screening assessments. This must be documented in the participant's source documents with the new participant number assigned.

8.1.1 Eligibility screening

8.1.1.1 Hepatitis screen, HIV screen

All ofatumumab treated participants will be screened for Hepatitis B surface antigen (HBsAg) and, if standard local practice, Hepatitis B core antigen (HBcAg).

Evaluation for HIV seropositivity will be performed in ofatumumab treated participants, and, if positive, confirmation by a second technique available at the laboratory site (e.g. Western blot). Appropriate counseling will be made available by the Investigator in the event of a positive confirmatory test. Notification of state and federal authorities, as required by law, will be the responsibility of the Investigator. This will be recorded as source data only by the use of an "S" for the corresponding criteria in [Table 8-1](#) (Assessment Schedule) of the protocol.

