14. Patients with active infections including systemic bacterial, viral (including SARS-CoV-2/COVID-19) or fungal infections, or known to have AIDS or to test positive for HIV antibody at Screening
15. Patients with neurological findings consistent with Progressive Multifocal Leukoencephalopathy (PML), or confirmed PML
16. Patients with IgG or IgM levels below LLN at Screening
17. Patients that have received any live or live-attenuated vaccines within 4 weeks prior to first dose of study drug administration
18. Patients at risk of developing or having reactivation of hepatitis: Positive results at Screening for serological markers for hepatitis (H) B indicating acute or chronic infection:
 - a. HBs Ag and/or anti-HBc IgM and/or HB virus deoxyribonucleic acid (DNA)
 - b. anti-HBs negative and Anti-HBc positive

NOTE: If the Investigator suspects false positive hepatitis serology results, such as an antibody pattern indicating acute hepatitis infection but no corresponding elevated liver enzymes and no signs or symptoms of liver disease, an infectious disease expert may be consulted. If the infectious disease expert finds no evidence of acute or chronic hepatitis infection and considers the serology results false positive and not clinically relevant, the Investigator must document (in source data) that the serology results are considered false positive and may then enroll the patient.

6 Treatment

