Hepatitis markers	
HBV screening is required in all participants, including Hepatitis B surface antigen (HBsAg) and hepatitis B core antibody (HBcAb) testing.
 
Participants with positive hepatitis B serology (either HBsAg or HBcAb) should consult a liver disease expert before the start of treatment and should be monitored and managed following local medical standards to prevent HBV infection or reactivation.
 
NOTE: If the infectious disease expert finds no evidence of acute or chronic hepatitis infection and considers the serology results false positive and not clinically relevant, the Investigator must document (in source data) that the serology results are considered false positive and may then enroll the participant.

Pregnancy Test	Serum / Urine pregnancy test (refer to Section 8.4.2).

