Hepatitis B virus (HBV) screening is required in all study participants, including hepatitis B surface antigen (HBsAg) and hepatitis B core antibody (HBcAb) testing. These can be complemented with other appropriate markers as per local guidelines. Participants with positive hepatitis B serology (either HBsAg or HBcAb) should consult a liver disease expert before the start of treatment and should be monitored and managed following local medical standards to prevent HBV infection or reactivation. In participants with suspicion of HBV infection (active/reactivation) during the study, laboratory testing for HBV should be done. For participants with positive hepatitis B serology (either HBsAg or HBcAb), the Investigator should consult a liver disease expert, and participants should be monitored and managed following local medical standards to prevent HBV infection or reactivation. In participants who develop infection or reactivation of HBV while receiving study drug, immediately discontinue study drug and institute appropriate treatment and follow-up.

[REDACTED]

[REDACTED]

[REDACTED]

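### Protocol 8.1.1.1 misstates the hepatitis B eligibility screen: it names core antigen, subject to local practice, where the rest of the protocol needs core antibody in every case

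*Protocol*

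**What the plan says.** Four places in the protocol bear on the hepatitis B screen.

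- **Section 8.1.1.1**, under eligibility screening, requires HBsAg in ofatumumab participants. It adds a second marker only "if standard local practice, Hepatitis B core antigen (HBcAg").
- **Table 8-4** in section 8.4.1 states: "HBV screening is required in all participants, including Hepatitis B surface antigen (HBsAg) and hepatitis B core antibody (HBcAb) testing".
- **Section 16.1.2** says the same: "Hepatitis B virus (HBV) screening is required in all study participants, including hepatitis B surface antigen (HBsAg) and hepatitis B core antibody (HBcAb) testing". It then allows more: "These can be complemented with other appropriate markers as per local guidelines".
- **Section 5.2, exclusion 18**, acts on positive serology at screening. Limb (a) lists "HBs Ag and/or anti-HBc IgM and/or HB virus deoxyribonucleic acid (DNA"). Limb (b) is "anti-HBs negative and Anti-HBc positive". The protocol summary repeats the criterion.

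Table 8-1 has a single hepatitis B row, at screening, for ofatumumab participants. It is marked as recorded in source documents only. Footnote 9 to that table asks for the blood to be drawn early enough for results to be known before the first dose.

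**The concern.** Section 8.1.1.1 is where a site looks for the hepatitis screening rule, and what it says differs from the other sections in two ways. The marker is an antigen instead of an antibody, and the obligation is left to local practice instead of being fixed. A site that met 8.1.1.1 to the letter could screen with HBsAg alone and hold no anti-HBc result.

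The stake is safety. Section 16.1.2 reports hepatitis B reactivation, some of it fatal, with ofatumumab in chronic lymphocytic leukemia at much higher intravenous doses, and reactivation with other anti-CD20 antibodies. It reports none in MS patients on ofatumumab. The sponsor nevertheless made 18b an exclusion, and dosing can run to Month 30 in the extension.

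**Working it through.** No arithmetic applies. The check is whether each version of the screen supplies the results that exclusion 18 needs.

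| Place | Surface antigen | Core marker | Condition on core marker | Anti-HBs named |
|---|---|---|---|---|
| 8.1.1.1 | yes | antigen (HBcAg) | only where local practice | no |
| Table 8-4 | yes | antibody (HBcAb) | none | no |
| 16.1.2 | yes | antibody (HBcAb) | none | no |
| Exclusion 18a | yes | antibody, IgM class | and/or list | no |
| Exclusion 18b | no | antibody (anti-HBc) | none | yes |

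1. **Marker.** Every other place that names a core marker names the antibody. Core antigen appears in no limb of exclusion 18, so an HBcAg result would not decide any eligibility criterion. The error is therefore in 8.1.1.1 and not in the other sections.
2. **Condition.** Table 8-4 and 16.1.2 make the core marker part of required screening. Section 8.1.1.1 makes it depend on the site.
3. **Screen run to the 8.1.1.1 minimum.** An HBsAg-positive patient is caught by 18a. For an HBsAg-negative patient there is no anti-HBc result, so 18b cannot be assessed, whether or not the site adds core antigen.
4. **Screen run to Table 8-4.** An HBcAb-negative patient does not meet 18b. An HBsAg-negative, HBcAb-positive patient meets 18b if anti-HBs is negative and does not if it is positive, so one more result is needed.
5. **Screen with anti-HBs added in HBcAb-positive patients.** 18b is decided in every case.

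Step 3 is the main defect. Step 4 is a smaller one: the criterion itself names anti-HBs, but no test list does. No gap is claimed for anti-HBc IgM or HBV DNA, because the and/or wording of 18a need not require them in everyone.

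**The case against.** The strongest reply is that 8.1.1.1 sets a floor and forbids nothing. A site running HBsAg and HBcAb under Table 8-4 also satisfies 8.1.1.1, and since the protocol uses the antibody everywhere else, HBcAg looks like a drafting slip. Harm needs a site to read 8.1.1.1 and ignore exclusion 18, Table 8-4 and 16.1.2. Footnote 9 ties the results to eligibility before dosing. Section 11.3 has monitors fully verify the inclusion and exclusion criteria. Section 16.1.2 calls for testing if infection or reactivation is suspected on treatment, and for stopping the drug at once if either develops.

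Much of this stands, and it is why the practical consequence is uncertain. It does not make 8.1.1.1 correct. Exclusion 18 acts on positive results, and a test that was not run gives none. Monitors can confirm 18b only if the results exist.

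On anti-HBs the reply is stronger. A reader might infer that 18b cannot be applied because no test list names the marker. The documents do not support that. The criterion itself calls for the result, the lists are introduced as non-exhaustive, 16.1.2 permits further markers, and Table 8-4 is plainly not a complete list of screening tests, since HIV is tested but has no row there. The central laboratory manual, not provided, may cover it. What remains is a clarification.

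A reader might also see a conflict between exclusion 18 and the instruction that "Participants with positive hepatitis B serology (either HBsAg or HBcAb) should consult a liver disease expert before the start of treatment". There is none to correct. The exclusion applies without a cross-reference, and the consultation has a consistent use in patients who are HBcAb positive and anti-HBs positive, whom 18b does not bar.

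**Conclusion.** Section 8.1.1.1 states a wrong marker and a wrong condition in a safety eligibility screen. That conclusion rests on the current protocol text alone and is firm. The missing mention of anti-HBs is real but secondary.

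A reader might go on to infer that barred patients were enrolled. Nothing in the documents shows this. They give no prevalence, no screening results and no laboratory manual, so the number of patients missed, if any, is unknown. The primary analysis, a proportion achieving NEDA-3 with an exact confidence interval, is not affected.

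Severity is minor to should-fix: the text is clearly wrong and cheap to correct, and partial safeguards surround it.

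**What to change.** - In 8.1.1.1, replace HBcAg with HBcAb and delete the local-practice condition.
- In 8.1.1.1 and Table 8-4, add that anti-HBs is obtained before first dose in any ofatumumab participant who is HBcAb positive, so that 18b can be decided.
- If enrolment is complete, confirm from source documents that HBcAb was obtained in each ofatumumab participant, and anti-HBs where HBcAb was positive. Start with those still on drug. Completion is likely but is an inference: the second SAP amendment is dated 22-Apr-2025, ahead of the Month 18 database lock. Because the hepatitis row of Table 8-1 is source-only, the clinical database is not planned to hold these results.

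The cost is a wording change in two places, possibly one further marker in HBcAb-positive participants from the screening blood draw, and a check covering the planned 118 ofatumumab participants within the eligibility verification that monitors already perform.
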